11. INFORMED CONSENT PROCESS

Informed consent must be obtained from the participant before any protocol-related activities are performed. Participants must be provided with a signed copy of the consent form. The eCRFs will be updated that the informed consent form has been signed.

12. ADVERSE EVENTS

Adverse event (AE) is defined as any unfavorable and unintended medical change, temporally associated with the use of the sponsor's product, whether or not considered related to the use of the product. Any worsening (i.e., any clinically significant adverse change in frequency and/or intensity) of a preexisting condition which is temporally associated with the use of the sponsor's product, is also an adverse experience. An adverse device effect (ADE) is an adverse event related to the use of the investigational device. In this study the ADE refers to side effect and complications.

A serious adverse event (SAE) is defined as an adverse event that leads to

- a) death,
- b) serious deterioration in the health of the subject, that either resulted in
 - 1) a life-threatening illness or injury, or
 - 2) a permanent impairment of a body structure or a body function, or
 - 3) in-patient or prolonged hospitalization, or
 - 4) medical or surgical intervention to prevent life-threatening illness or injury or permanent impairment to body structure or body function

	QMS document Nerivio TCH-008 Clinical Study Protocol	Doc ID: TEC0250 Revision #: 3.0 Page: 52 of 58
---	--	--

c) fetal distress, fetal death or a congenital abnormality or birth defect

A serious device related adverse effect (SADE) is an adverse event related to the use of the investigational device and that is considered by regulations and definitions as serious.

12.1. Characteristics of AEs

An investigator who is a qualified physician, will evaluate all adverse events as to:

Maximum intensity

Mild: awareness of symptom, but easily tolerated

Moderate: definitely acting like something is wrong

Severe: extremely distressed or unable to do usual activities

Duration

Record the start and stop dates of the adverse experience. If less than 1 day, indicate the appropriate length of time and units.

Relationship of an AE and SAE to the study device

The relationship of the adverse event to the study device is defined as:

Definitely related: There is evidence of exposure to the device. The temporal sequence of the AE onset relative to use of the device is reasonable. The AE is more likely explained by the device than by another cause. Dechallenge is positive. Rechallenge (if feasible) is positive. The AE shows a pattern consistent with previous knowledge of the device.

Possibly related: There is evidence of exposure to the device. The temporal sequence of the AE onset relative to use of the device is reasonable. The AE could have been due to another equally or less likely cause. Dechallenge (if performed) is positive.

Probably related: There is evidence of exposure to the device. The temporal sequence of the AE onset relative to use of the device is reasonable. The AE is more likely explained by the device than by another cause. Dechallenge (if performed) is positive.

Unlikely related: The relationship with the use of the device seems not relevant and/or the event can be reasonably explained by another cause, but additional information may be obtained.

Definitely not related: The subject/patient did not use the device; or temporal sequence of the AE onset relative to device use is not reasonable; or there is another obvious cause of the AE.

	QMS document Nerivio TCH-008 Clinical Study Protocol	Doc ID: TEC0250 Revision #: 3.0 Page: 53 of 58
---	--	--

12.2. Reporting of AEs and SAEs

All adverse events will be recorded in appropriate adverse events case report form. The adverse events will be used for the safety assessment. An on-site visit to monitor the adverse event will be conducted if the principal investigator determines it is needed. These visits will be reported using designated case report forms. If during the last visit, an ongoing device-related AE is present, the participant will be monitored for approximately 2 weeks, until the AE resolves or a steady state is achieved.

The PI must report any SAE or SADE to the sponsor within 1 business day:

Theranica Bioelectronics

[name]

[contact]

Fax: [name]

Email: [contact]

The sponsor is responsible for reporting the adverse events to regulatory agencies, IRB/IECs, and investigators in accordance with all applicable global laws and regulations.

12.3. Anticipated device-related AEs

Possible adverse events associated with remote electrical neuromodulation include, but are not limited to, the following:

- Numbness of the hand/arm
- Itching
- Muscle spasms
- Redness
- Warmth sensation
- Tingling
- Pain in the arm

All anticipated device-related AEs, if present, are temporary and should disappear shortly after the treatment.

The following migraine symptoms are foreseeable and will not be considered as device related: headache, nausea, light sensitivity, sensitivity to noise, allodynia, abdominal pain, loss of appetite, cold or heat sensation, paleness, fatigue, dizziness, anxious mood, fever (rare), blurred vision, vision symptoms such as bright flashing dots or lights, blind spots, wavy or jagged lines (aura).

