	
patient consumes at least one dose of any medication (OTC or prescribed) for acute treatment of headache or migraine.
 
[Endpoints 2-6 below relate to the pre-emptive follow-up phase]
 
2. Percentage of patients who treat for the first treatment in the pre-emptive phase, during a prodrome, when they are pain free, and remain pain free during the following 2 hours after the treatment, without use of acute medication.3. Percentage of patients who treat for the first treatment in the pre-emptive phase, during the prodrome, when they are pain free, and remain pain free during the following 24 hours after the treatment, without use of acute medication.4. Percentage of patients who treat for the first treatment in the pre-emptive phase, during the prodrome, when they are pain free, and remain either pain free or with mild pain during the following 24 hours after the treatment without use of acute medication.5. Mean change in the percentage of prodromes which were followed by a headache within 24 hours from baseline to the end of the pre-emptive follow-up phase.6. Mean change in the average number of moderate/severe headache days per month in the pre-emptive phase compared to the 4-week baseline phase. 
[Endpoint 7 relate to Health Economics analysis]
 
7. Differences between active and sham groups in reduction of the following events from baseline (weeks 1-4) to the last 4 weeks of treatment phase (weeks 9-12): (a) Absenteeism, (b) Presenteeism, (c) Healthcare provider appointments, (d) ED/ER visits, (e) Brain MRI/CT scans 
[Endpoint 8 relate to migraine prediction analysis]
 
8. Feasibility of a migraine prediction algorithm: Analysis of the daily information provided by the participants during the baseline period (weeks 1-4) for the purpose of predicting their migraine days
Safety endpoints	
1. The incidence of adverse events in general and by seriousness, severity and association to the device.2. Treatment tolerability (by electronic patient report).

theranica	QMS document Nerivio TCH-008 Clinical Study Protocol	Doc ID: TEC0250 Revision #: 3.0 Page: 13 of 58
------------------	--	--

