6.4.4. Safety endpoints

1. Device safety
The incidence of adverse events in general and by seriousness, severity and association to the device.
2. Treatment tolerability
The percent of subjects who fail to complete the study because of device-related adverse events.

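### Section 12.3 rules out device-relatedness by symptom term, conflicts with the causality assessment in 12.1, and can only lower or leave unchanged the device-related safety counts

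*Combined protocol and SAP*

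**What the plan says.** Four parts of the combined protocol and SAP bear on how an AE is attributed to the device.

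- Section 12.1 gives the task to the investigator: "An investigator who is a qualified physician, will evaluate all adverse events as to" intensity, duration and relationship to the device. Relationship is graded on five levels using exposure, timing, alternative causes, dechallenge and rechallenge. One criterion reads "The temporal sequence of the AE onset relative to use of the device is reasonable". No symptom is exempted.
- Section 12 includes in the AE definition "Any worsening (i.e., any clinically significant adverse change in frequency and/or intensity) of a preexisting condition" when it is temporally associated with product use.
- Section 12.3 lists anticipated device effects, among them warmth sensation, and then adds a second list: "The following migraine symptoms are foreseeable and will not be considered as device related". That list includes headache, nausea, light and noise sensitivity, allodynia, anxious mood, blurred vision and "loss of appetite, cold or heat sensation, paleness, fatigue, dizziness".
- Section 6.4.4 defines device safety as "The incidence of adverse events in general and by seriousness, severity and association to the device", and tolerability as "The percent of subjects who fail to complete the study because of device-related adverse events". The synopsis words tolerability differently: "Treatment tolerability (by electronic patient report)".

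**The concern.** Sections 12.1 and 12.3 give different answers for the same event. Suppose a participant becomes dizzy during a session, recovers when stimulation stops, and is dizzy again at the next session. Under 12.1 an investigator could grade this as definitely related. Under 12.3 it cannot be device related, because dizziness is on the list. Likewise, a clinically significant worsening of headache is an AE under section 12, but 12.3 bars its attribution to the device.

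The design makes timing informative. Section 6.3 schedules stimulation every other day whether or not there is a headache, and bars use of the device as acute treatment. Participants qualify with 6 to 24 headache days in the 28-day baseline, so at baseline they have between 28 − 24 = 4 and 28 − 6 = 22 days without headache. Some sessions can therefore be expected on headache-free days. A listed symptom arising just after such a session is the case in which timing helps most, and the 12.3 rule discards that information.

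At stake are the outputs that need a relatedness call: the device-related part of safety endpoint 1, tolerability as defined in 6.4.4, the device-related summaries in 7.2.4 and 7.6.4, the serious device-related category in section 12, and the roughly two-week follow-up in 12.2 of device-related AEs still present at the last visit. Attribution matters most in the open-label follow-up phase, where everyone has an active device and there is no concurrent sham arm.

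**Working it through.** **Step 1: is there a figure to reproduce?** No. The plan states no expected device-related AE rate for this trial, so the check is mainly a comparison of sections.

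**Step 2: which outputs depend on the relatedness call?**

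| Output | Section | Depends on 12.3? |
|---|---|---|
| AEs by association to the device | 6.4.4, 7.2.4, 7.6.4 | Yes |
| Non-completion because of device-related AEs | 6.4.4 | Yes |
| Serious device-related effects | 12, 7.6.4 | Yes |
| Follow-up of ongoing device-related AEs | 12.2 | Yes |
| Recording of AEs, overall incidence, incidence by type | 12.2, 6.4.4, 7.6.4 | No |
| Reporting of serious AEs to the sponsor | 12.2 | No |
| Non-completion for any reason or any AE, time to withdrawal | 7.6.4 | No |
| Tolerability by electronic patient report | Synopsis | Not directly |
| Migraine and headache day endpoints | 6.4.1, 6.4.2 | No |

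**Step 3: direction.** Let f be the share of truly device-related events that fall under listed terms. Taken literally, the rule gives

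reported rate = true rate × (1 − f), with 0 ≤ f ≤ 1.

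The reported rate never exceeds the true rate, and equals it only when f = 0 (or the true rate is zero). The same factor shrinks the between-arm difference if f is equal in both arms.

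**Step 4: size, as illustration only.** The only sham-controlled device-related rates given by arm are those of the pivotal acute-treatment study TCH-003 (section 4.2.2): 6/126 = 4.8% active and 3/126 = 2.4% sham. Fisher's exact test on these counts gives p = 0.4998, as the protocol states. Assume these rates apply here and that f is equal in both arms. Nothing in the documents gives f, so the whole range is shown.

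| f | Active | Sham | Difference (points) |
|---|---|---|---|
| 0% | 4.8% | 2.4% | 2.4 |
| 25% | 3.6% | 1.8% | 1.8 |
| 50% | 2.4% | 1.2% | 1.2 |
| 75% | 1.2% | 0.6% | 0.6 |
| 100% | 0% | 0% | 0 |

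**Step 5: do the prior data place f?** Barely. The device-related events described in TCH-004 and TCH-006 were arm pain, and section 4.3.2 says the pivotal study's AEs were mainly warmth, redness and numbness of the arm or hand. These point to a small f. The single device-related event in TCH-005 resolved after a triptan, but its symptom is not named. If it was a listed symptom, which is only an inference, this rule would take that study from 1/42 = 2.4% to 0/42.

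**The case against.** The strongest reply is that 12.3 speaks of migraine symptoms, and so covers only symptoms that form part of a participant's migraine. That would fit 12.1, where another obvious cause supports a grade of definitely not related. It may well be the intention, but the text does not say it. The rule is written by term, is mandatory in form, and is not limited to the participant's usual migraine. If guidance was meant, the wording should show it.

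A second reply is that nothing is hidden, and much of this stands. A reader might infer that more headaches or dizziness after stimulation would vanish from the safety results. The documents do not support that. Every AE is recorded, incidence is reported in total and by type, serious AEs reach the sponsor whatever their attribution, and the data monitoring committee reviews safety data. Worsening headache would also show in the sham-controlled primary and secondary endpoints. Only the device-related rows would be empty for listed terms. The efficacy diary is not a full substitute, though: the migraine-day definition does not cover dizziness, fatigue, anxious mood or abdominal pain.

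Third, the overlap of warmth and heat sensation looks like a flat contradiction but may not be one. Warmth appears beside arm and hand effects, heat beside paleness and fever, so a local versus general distinction is plausible. It is not stated, and needs only a clarification.

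Fourth, the effect on tolerability holds for the 6.4.4 definition. The synopsis version and the any-AE discontinuation summary in 7.6.4 are not directly touched.

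**Conclusion.** The point holds as an internal conflict with a one-directional consequence. Section 12.3 cannot be followed literally together with 12.1, no precedence is stated, and sites could classify the same event differently. Where 12.3 is followed, the four dependent outputs marked in the table can be too low but never too high.

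The size is unknown. Downward bias is a possibility here, not an established fact: with f = 0 there is none, and most prior device-related events that are described were local arm effects. The rates in the illustration rest on carrying TCH-003 over to preventive use and on an f that no document supplies, so they are not an estimate for this trial. The documents likewise do not support reading the conflict as a flaw in the overall safety evaluation, because the all-cause summaries remain available. It is worth correcting before the analysis, but it does not threaten the trial's main conclusions.

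**What to change.** Amend section 12.3 in three respects.

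1. Replace the statement that the listed symptoms are not device related with one saying that they are expected in the underlying disease, and that the investigator still assesses relationship under 12.1, blinded to arm in the treatment phase, including for worsening from baseline. The list can stay as information for assessment and coding.
2. State how warmth sensation as a device effect differs from heat sensation as a migraine symptom, for example by body location if that is what is meant.
3. Add to 7.6.4 a table of the listed symptoms by arm, regardless of attribution. That section already plans AEs by type, but does not explicitly say by arm.

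The tolerability definition should also be made the same in the synopsis, 6.4.4 and 7.6.4, so that it is clear which version depends on attribution.

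The cost is a short text amendment, with no change to design, sample size or data collection. The downside for the sponsor is that the device-related AE rate may look slightly less favourable.

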12.4. Device malfunction

Device malfunction is an inadequacy of the device with respect to its identity, quality, durability, reliability, safety, or performance, such as failure, use error or inadequate labeling. Device malfunctions may or may not be associated with an adverse event.

	QMS document Nerivio TCH-008 Clinical Study Protocol	Doc ID: TEC0250 Revision #: 3.0 Page: 54 of 58
---	--	--

All device malfunctions will be reported in the eCRF. Device malfunctions that were associated with an SAE or that could have led to an SAE if a) suitable action had not been taken or b) intervention had not been made or c) if circumstance had been less fortunate, will be reported within 24 hours of occurrence. If possible and needed, the device(s) associated with malfunction or failure will be retained until arrangements for its collection are made by the sponsor.

All device malfunctions will be summarized and reported in the clinical study report and will be reported to the regulatory authorities according to local reporting requirements.

13. EARLY TERMINATION

13.1. Criteria and procedures

The study may be discontinued if:

The sponsor decides to terminate the study due to company considerations (e.g. the data monitoring committee recommends terminating the study based on the interim analysis)

If in the opinion of study PI, the study presents an unreasonable medical risk to the patients, the PI may close the site under his/her responsibility.

If the clinical investigation terminated early or suspended, the sponsor will send a report justifying this decision to the corresponding IRB/EC, regulatory body and all investigators. A suspended or terminated clinical investigation may not be re-initiated without approval of the corresponding IRB/EC and relevant RA, as applicable. Enrolled subjects will be followed according to the institution's standards and guidelines.

13.2. Requirements for patient follow-up in case of withdrawal

If a patient withdraws consent, all efforts will be made to collect the final visit observations as soon as possible.

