6.1.3. Withdrawal / Discontinuation

Participants may withdraw consent at any time and do not have to provide an explanation.

Participant may be withdrawn from the study by the PI or sponsor due to one or more of the following reasons:

- Participant is lost to follow-up
- Refusal of the participant to continue treatment and/or follow-up observations

	QMS document Nerivio TCH-008 Clinical Study Protocol	Doc ID: TEC0250 Revision #: 3.0 Page: 32 of 58
---	--	--

- Serious adverse event
- Participants encountering difficulties with the investigational product (IP) (e.g. cannot tolerate the treatment, unable to operate the application)
- Significant protocol deviation/violation or noncompliance, either by the patient or the investigator
- Decision made by the investigator that termination is in the patient's best medical interest
- Device malfunction
- Other ethical or clinical considerations upon investigator discretion

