All other patients will be offered to receive an active device and continue in a safety follow-up, using Nerivio for preventive treatment of migraine, as instructed in the treatment phase.

Follow-up phase (open label):

Participants who continue into this 4-week period of follow-up phase, will receive an active device. Those who do not meet the requirements (see above) will use Nerivio for preventive treatment of migraine, as performed during the treatment phase. Participants will continue to complete a daily diary and use the device every other day for 45 minutes.

Participants who meet the requirements (see above) will receive the device for preemptive treatment of migraine. Participants will be instructed to use Nerivio within 60 minutes of prodrome symptoms onset, prior to the start of a headache, for a 45-minute treatment. The participants will be instructed to complete questionnaires regarding their headache, prodrome symptoms, and medication use at baseline (start of treatment), 2 hours post-treatment and 24 hours post-treatment. In addition, participants will be instructed to continue to complete the daily diary as in the baseline and treatment phases.

Participants will be permitted to take their usual care medications during this phase, except for the timepoint between starting a device treatment until 2 hours after treatment start.

Fourth (final) visit – End of study:

During the final visit, participants may be asked to fill additional questionnaires on their migraine and their experience with the device. In addition, all study devices will be returned to the clinic, either in person or by mail/shipment.

Study design is summarized in Figure 4 below.

[figure not shown]

Figure 4: Study design

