7.4. Sample size

A sample size of 234 participants, 117 per each treatment arm, was determined to provide 80% power to detect a mean ($\pm SD$) difference of 2 ± 3.0 in the reduction in number of migraine headache days from the baseline to weeks 9-12 of the treatment phase, between the active group and the sham group at a two-sided alpha level of 0.05. With an anticipated discontinuation rate of about 35%, up to 375 participants are planned to be enrolled. In case of higher dropout or non-eligible participants or missing data, enrollment may be extended in order to reach the desired sample size.

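### Stopping the device is not separated from leaving the study, so week 9-12 outcomes of people who stop may go uncollected, which weakens the ITT interim look and any all-randomized sensitivity analysis

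*Combined protocol and SAP*

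**What the plan says.** Section 6.1.3 begins with the participant's own right: "Participants may withdraw consent at any time and do not have to provide an explanation". It then gives a second route out: "Participant may be withdrawn from the study by the PI or sponsor due to one or more of the following reasons". The listed reasons include "Refusal of the participant to continue treatment and/or follow-up observations" and "Participants encountering difficulties with the investigational product (IP) (e.g. cannot tolerate the treatment, unable to operate the application", as well as noncompliance and device malfunction.

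Section 13.2 is a single sentence. Its trigger is "If a patient withdraws consent", and its instruction is that "all efforts will be made to collect the final visit observations as soon as possible". Section 6.3 describes the fourth visit as the final one: "During the final visit, participants may be asked to fill additional questionnaires on their migraine and their experience with the device". Apart from that, devices are returned.

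The outcomes are collected elsewhere. The primary endpoint counts migraine headache days in the daily app diary over weeks 9-12 (6.4.1, 7.2.1). HIT-6 and MSQ for those weeks are completed at the third visit (6.3).

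ITT is everyone randomized. The primary efficacy set is mITT, which needs at least 22 diary days and at least 12 treatments in weeks 9-12 (7.5, 7.6.3). The interim futility look uses both sets (7.6.7). Section 7.4 plans for attrition: "With an anticipated discontinuation rate of about 35" per cent, with up to 375 enrolled.

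**The concern.** Stopping treatment and ending observation are different events. An all-randomized analysis needs outcomes from people who stop the device, and they are likely to differ from those who continue, since poor effect and poor tolerance are ordinary reasons to stop. Section 6.1.3 merges the two events, and 13.2 supplies no data for most of the people concerned. If their week 9-12 diary is not kept, the ITT result at the interim rests on whatever imputation is chosen, and that look can stop enrolment. The same holds for any all-randomized check on the mITT result at the end. Diary days that were never recorded cannot be reliably recovered later.

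**Working it through.** **1. Which situations have a data rule.**

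| Situation | 6.1.3 | Efficacy data asked for in 13.2 |
|---|---|---|
| Withdraws consent | Participant's right | Final visit observations |
| Refuses the device, would keep the diary | May be withdrawn | None |
| Cannot tolerate the device | May be withdrawn | None |
| Noncompliance or malfunction | May be withdrawn | None |

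No section asks someone off the device to keep the diary to week 12.

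**2. What a final visit would supply.** The primary endpoint and secondary endpoints 1 to 3 come from the diary. Secondary endpoints 4 and 5 come from visit 3. Full compliance with 13.2 would supply none of them.

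**3. What the analysis rules can repair.** Section 7.6.6 prorates: migraine days / reported days x 28. Its example reproduces: 7/24 x 28 = 8.17. With no reported days in weeks 9-12 the formula is undefined. Section 7.2.1 promises several possible imputation methods, names none, and does not say which analysis set they apply to.

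**4. Which analyses are affected.** On an every-other-day schedule, the twelfth treatment of weeks 9-12 falls on day 1 + 2 x 11 = 23 (or day 24 if the first is on day 2). Someone who stops before then is outside mITT however complete the diary. The affected analyses are therefore the interim on ITT and any all-randomized sensitivity analysis.

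**5. How many people.** I take 234 evaluable participants as given; whether that number follows from its own inputs is a separate question. 234/(1 - 0.35) = 360. The stated 375 allows for 1 - 234/375 = 37.6%, which is compatible with wording that is only approximate.

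- Upper bound at the plan's rate: 0.35 x 375 = 131. The 375 are enrolled at visit 1, before the 4-week baseline and before randomization at visit 2, so some of the 131 may never enter ITT.
- Interim, same rate applied wholly after randomization and 84 taken as evaluable: 84/0.65 = 129 randomized, about 45 without outcomes. This too is an upper figure.
- For contrast, two earlier studies of this device summarised in 4.2. TCH-004: 60 enrolled, 45 used the device, 39 analysed. Total loss is 21/60 = 35%, but after first use only 6/45 = 13%. TCH-006: 99 in the safety denominator, 91 analysed, a loss of 8/99 = 8%. At those rates the interim figure is 84 x 45/39 - 84 = 13, or 84 x 99/91 - 84 = 7. These were open-label acute-treatment studies, so they are illustrations only.

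**6. Why it can matter at the interim.** Assume a share p is missing equally in both arms and that people who stopped show no active-sham difference. The all-randomized difference is then (1 - p) x the completers' difference. Against the 1-day threshold in 7.6.7, completers and all randomized fall on opposite sides when the completers' difference lies between 1 and 1/(1 - p):

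- p = 8% (8/99): 1 to 1.09 days
- p = 13% (6/45): 1 to 1.15 days
- p = 35%: 1 to 1.54 days

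Both p and the zero difference are assumptions.

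**The case against.** Withdrawal under 6.1.3 is discretionary. Section 6.3 gives diary instructions for the whole 8 weeks, section 6.7 has missing reports trigger automatic queries, and partial diaries are prorated. Participants who used the device too little for the pre-emptive phase are still offered safety follow-up, so the protocol does contemplate low users staying. All of this stands. It means outcomes may not be collected, not that they are lost.

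One could also read the final visit in 13.2 as an exit visit with the visit 3 questionnaires. Section 6.3 does not say so. A visit held as soon as possible after someone leaves in the first weeks would in any case precede weeks 9-12, and no visit replaces a 28-day diary.

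Three stronger readings are tempting:

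- A reader might infer that about 131 randomized participants will lack the primary outcome. The documents tie 375 to enrolment, not randomization.
- A reader might infer that the planned result overstates the effect by a known amount. If the missing participants' active-sham difference were 1 to 2 days less favourable, the gap would be 0.35 x 1 = 0.35 to 0.35 x 2 = 0.70 days, or at 8% to 13% missing, 0.08 to 0.27 days. The 1 to 2 days are assumed, and for the final analysis the gap would come from the mITT definition, not from the follow-up rule.
- A reader might infer that 13.2 seeks data against a participant's wishes. The text sets no condition on agreement, but a person who withdraws may still agree to a visit, and the consent pages are not available to check.

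Section 13.2 is also not the only follow-up rule of any kind: 12.2 monitors an ongoing device-related adverse event for about 2 weeks. That is safety follow-up only.

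**Conclusion.** The gap is real and should be closed. The plan has no status for a participant who is off the device and still followed. Its one rule on efficacy data after leaving addresses withdrawal of consent and asks for a visit that contains none of the week 9-12 outcomes.

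The consequence is confined to the ITT interim futility analysis and to any all-randomized sensitivity analysis of the primary endpoint. The planned final efficacy analysis on mITT would not change.

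The number affected is not given. About 131 overall and about 45 at the interim are upper figures at the plan's own 35%; post-randomization losses of 8% to 13% would put the interim figure at about 7 to 13. No bias figure can be derived from the documents.

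**What to change.** In 6.1.3 and 13.2, define two situations.

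(a) Withdrawal of consent: no further efficacy data are collected unless the participant agrees, and safety follow-up proceeds as in 12.2 to the extent the participant permits.

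(b) Stopping the device with continued consent: the participant is asked to keep the daily app diary to week 12 and to complete visit 3, remotely if needed.

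In 7.6.7 and 7.2.1, state that people in (b) enter the ITT interim analysis and an all-randomized sensitivity analysis of the primary endpoint with their observed data. No rule on when treatment stops needs to change.

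The cost is amendment wording plus some extra diary reminders and follow-up for people off the device. The diary is already on the participant's own phone, and 6.3 allows every visit to be remote. The change recovers nothing from people lost to follow-up or unable to use the app, and it leaves the mITT analysis as it is.
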